### **7.2.6. KNOWLEDGE TASKS EVALUATION**

The knowledge tasks evaluation will take place once the Post-Test Debriefing Interview is complete. The knowledge tasks evaluation commences with the Study Observer requesting that the user read through the Installation and Proper Use Reference Guide and all other labeling information contained on the device and the packaging regardless of whether or not he or she did so during the use evaluation study component. The Study Observer will not point out any specific information in any of these materials to be read or noted, and although the Study Observer will record any questions asked by the user during the material review process, he or she will not answer any questions the user may ask or otherwise interfere with the process in any manner.

Once the user indicates that he or she has completed reading the supplied materials, the Study Observer will administer the Knowledge Task Patient User Questionnaire (**Appendix G**). The Study Observer will record verbatim the user's responses to each question but will otherwise not react to the user's responses. The Study Observer will not explain or reword any of the pre-established questions in the Knowledge Task Patient User Questionnaire and will not provide any guidance or feedback regarding the user's responses in any manner.

Following completion of the knowledge tasks evaluation, the user's participation in the study is complete.

## **8. REGULATORY AND ETHICAL CONSIDERATIONS**

### **8.1. DATA MANAGEMENT**

#### **8.1.1. Data Administration**

For each enrolled user, the Study Observer will be the only individual to record information on the study record forms and only the required data elements will be recorded. There will be no identifying information recorded that could potentially connect an individual user's data record to the individual. Unique de-identified codes will be used on each user's record forms.

The recorded data will only be used for the purposes of evaluating the objectives of this study. The sole parties who will have access to the record forms and the study data will be the Study Observer, the study Sponsor and the study analyst. Access to the record forms and data will not be given to outside parties at any time during the data collation and analysis process or in the future for any reason.

### **8.1.2. Compliance Statement**

The Study Observer will perform the study in accordance with this protocol. Collection and recording of data will be accurate and will ensure the privacy, health, and welfare of users during and after the data collection process.

## **8.2. INFORMED CONSENT**

### **8.2.1. Informed Consent**

This Human Factors Validation Testing study will operate under appropriate Investigational Review Board (IRB) approval and will meet Health Insurance Portability and Accountability Act (HIPAA) Privacy Requirements. Prior to study enrollment, each user partaking in the study will be required to voluntarily sign the study informed consent form following review of the form with the Study Observer. The informed consent form for this study is contained in **Appendix H**.

### **8.2.2. Confidentiality**

All data and record forms generated during this study will be kept confidential in accordance with HIPAA regulations on subject privacy. The Study Observer will not use the data and record forms for any purpose other than conducting the study. Coded de-identifiers will be used for all data entries.

## **8.3. RISK ASSESSMENT**

### **8.3.1. Potential Risks of Participation**

The only potential risk to subjects (users) in this study is breach of privacy and confidentiality. The application of a de-identified coding system to record subject data has been established to minimize this risk.

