### 4.1. STUDY DESIGN ELEMENTS

The key elements of the study design that support its ability to generalize study results to the intended user under intended use conditions are the following:

- (i) Users (test participants) will represent the intended (actual) users of the LunulaLaser™ OTC; that is, users will be employees at nail salons, beauty salons and spas, fitness and wellness centers, and the like;
- (ii) All critical tasks will be performed, observed and evaluated during the testing;
- (iii) The device user interface and all associated instructional/informational materials will represent the final intended post-clearance (actual use) design; and
- (iv) The simulated-use test conditions will be sufficiently realistic to represent the actual intended conditions of use. Under actual intended conditions of use, the user will receive the Erchonia LunulaLaser™ OTC device in its full packaging via delivery to the facility at which they are employed and will need to rely on the information/instructional information contained in the Installation and Proper Use Reference Guide and the device and packaging labeling to configure and operate the device for use.

(v) In this study, the user will simply be presented with the device in its intended packaging as if receiving it at their place of employment. No additional information, instruction or training will be provided by the Study Observer, or any other individual associated with the study. The user will be left to work out how to operate the Erchonia LunulaLaser™ OTC as independently and naturally as possible without interference or influence from the Study Observer. While the user will have received the instructional information in the packaging as in intended use, he or she will not be instructed to use any of the information. It will be up to the user as to if or how he or she chooses to use that information to set up operation of the device as would occur under actual conditions of intended use.

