## **5. CRITICAL TASKS ANALYSIS**

**5.1. CRITICAL TASK:** For the purpose of the critical tasks analysis for this study, a critical task is defined as a user task which, if performed incorrectly (use error) or not performed at all, would or could cause serious harm to the patient or user, where harm is defined to include compromised medical care (use-related hazard). Critical task analysis is part of the device risk analysis.

**5.2. USER TASK:** A user task is defined as an action or set of actions performed by a user to achieve a specific goal i.e., safe, and effective use of the device for the intended purpose.

**5.3. USE ERROR:** Use error is defined as a user action or lack of action that is different from that expected by the manufacturer and caused a result that was different from the result expected by the user; was not caused solely by device failure; and did or could result in harm.

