Safety Glasses	
The LUNULALASER™ OTC is classified by the FDA/IEC as a Class 2 laser device. This represents a current standard for use to ensure the safety of the client. A Class 2 laser is determined to have a chronic viewing hazard. Pointing the laser beam directly into the eye and maintaining it there for an extended period of time could prove to be damaging. To ensure there is no possible instance of residual effect, a pair of specialty safety glasses for use by the client during treatment is provided in the device packaging. The safety glasses, sufficiently and effectively block the laser light spectrum at OD 2+ @ 635nm, OD 0.75 @ 405nm VLT60.
 
Additionally, the following warning is included in the Installation and Proper Use Reference Guide:
 
 WARNING: The client should always be correctly fitted with the safety glasses provided before turning on the laser and doing any treatment.
 
Furthermore, Step 6 of the LunulaLaser™ OTC Treatment Protocol on page 17 of the Installation and Proper Use Reference Guide reads as follows: "Have your client put on the safety glasses..."

Logic of the overall user-system interaction, including how, when, and in what form information (i.e., feedback) is provided to the user.	
Set-up and use of the Erchonia LunulaLaser™ OTC device is designed to be inherently logical and sequential. Information, including visual confirmation via text and lights of user tasks performed are provided in real-time on the LCD and touch screen. These operations and interactions have also been designed with consideration of the design of comparable devices presently on the market.

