#### **6.4. STUDY OBSERVER**

The Study Observer is an Erchonia Corporation employee who is suitably qualified, trained and experienced in conducting Human Factors Validation Testing and is specifically trained to all aspects of the set-up, start-up and use of the Erchonia LunulaLaser™ OTC; and to the information contained in the Installation and Proper Use Reference Guide, and device and package labeling.

The Study Observer's sequential role in this study is to:

- (i) conduct the informed consent process with the user.
- (ii) conduct the study qualification evaluation with the user.
- (iii) observe the user's performance across each of the critical tasks associated with the process of using the LunulaLaser™ OTC from receipt of the packaged device through to operation and use of the device to administer a treatment, and to note his or her observations, including observations of use problems and errors and close calls, throughout the process on the respective Observation Forms.

The Study Observer is trained not to provide any guidance to the user through this process or to answer any questions, simply to observe and to record those observations, unless intervention becomes necessary for safety.

- (iv) conduct a post-test debriefing interview to collect the user's perspectives to supplement the observer's observations, including attaining the user's subjective assessment of any use

difficulties experienced throughout the process of setting up and operating the device; gathering specific feedback on each critical task; and investigating all use difficulties, errors and close calls observed and noted by the Study Observer during the test phase.

- (v) assess the user's understanding of the essential information contained in the Installation and Proper Use Reference Guide, and packaging and device labeling through administration of a knowledge task questionnaire.

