### **8.3.3. Risk-Benefit Assessment**

The Risk-Benefit assessment reveals no negatives in conducting this Human Factors Validation Testing.

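### Sections 8.3.1 and 8.3.3 leave out the laser viewing hazard that the protocol describes, and the visible consent and eligibility steps do not reach the treated clients

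*Combined protocol and SAP*

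**What the plan says.** **Risk statements.** Section 8.3.1: "The only potential risk to subjects (users) in this study is breach of privacy and confidentiality". Section 8.3.3: "The Risk-Benefit assessment reveals no negatives in conducting this Human Factors Validation Testing".

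**Hazard.** In the safety glasses entry of the table in 6.3, the protocol says: "A Class 2 laser is determined to have a chronic viewing hazard". It adds that pointing the beam into the eye and "maintaining it there for an extended period of time could prove to be damaging". One pair of glasses, for the client, is supplied. The user characteristics table in 6.1.1 expects the user to be able to fit glasses on both user and client.

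**Conduct.** Section 5.1 defines critical tasks as those which, done wrongly or left out, "would or could cause serious harm to the patient or user". Section 4.1 states: "All critical tasks will be performed, observed and evaluated during the testing". Section 6.4 says the observer is there "simply to observe and to record those observations, unless intervention becomes necessary for safety", and 7.2.4 repeats the safety exception. Section 8.1.2 commits to users' health and welfare as well as their privacy.

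**Clients.** The heading of 6.1 places users and clients together under subjects. Sections 6.1.2 and 6.1.2.1 draw clients from sponsor staff who do not work with the device. Section 7.2.4 has the user give the client a treatment, with a device that 7.2.3 says is supplied as it would be after clearance. Consent (7.2.1, 8.2.1) and eligibility (7.2.2) are written for users. The introduction to 7.2 mentions the treatment recipient where applicable, but no later step sets a client consent or check.

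**The concern.** An ethics board and a prospective participant both rely on the risk statement. If it says that privacy is the sole risk while the device description in the same protocol gives an eye hazard, the statement cannot support informed consent on that point.

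The client question matters for a related reason. Clients receive the treatment from users who have had no training on this device and who may choose not to read the Guide. Fitting the glasses, the main client protection visible in the text, is itself one of the user actions being observed. The other visible safeguard is the observer's power to intervene. Clients are employed by the sponsor, as is the observer, so a documented free choice to take part carries more weight than usual.

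What is at stake is accurate disclosure and participant protection, not the validity of the analysis.

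**Working it through.** No arithmetic applies. The check sets the sections against each other.

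**Step 1: scope of the two statements.** Section 8.3.1 makes a universal claim about users: one risk, privacy, and nothing else. Section 8.3.3 makes a universal claim about the whole study, with no restriction to users. One acknowledged physical risk, however small, is enough to make such a claim wrong.

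**Step 2: is a physical risk acknowledged?**

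- *Section 6.3* names a viewing hazard and says that sustained direct exposure could cause damage. It is discussed mainly as a client hazard, so it bears most directly on 8.3.3.
- *Section 6.1.1* expects glasses on the user too. This suggests that the sponsor does not regard the optical hazard as confined to the client, and it bears on 8.3.1.
- *Sections 6.4 and 7.2.4* suspend the no-interference rule for safety. That clause has no purpose if privacy is the only risk.
- *Sections 5.1 and 4.1* have users perform tasks defined by their potential for serious harm to patient or user. This is weaker support, because the definition is generic and counts compromised medical care as harm. The severity ratings are in Appendix A, which was not available.

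The first three are enough. Neither 8.3.1 nor 8.3.3 agrees with the rest of the protocol.

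**Step 3: how large is the risk?** Section 6.3 ties harm to prolonged direct viewing. Section 6.3 also has the client's foot placed in the device. Glasses are supplied for the client, and a trained observer is present. All this points to a low risk, and nothing in the documents allows it to be quantified.

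**Step 4: who is covered by the protections in the visible text?**

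| Element | Users | Clients |
|---|---|---|
| Listed as subjects (6.1) | yes | yes |
| Consent step (7.2.1, 8.2.1) | yes | not stated |
| Eligibility check by the observer (7.2.2) | yes | not stated |
| Welfare commitment (8.1.2) | yes | not stated |
| Risk statement (8.3.1) | privacy only | not stated |
| Glasses supplied (6.3) | not listed | one pair |

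The titles of Appendix D (eligibility forms) and Appendix H (consent form) name users only. Titles do not settle what the forms contain.

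**Step 5: is the laser live during testing?** Section 4 calls the design simulated use. Sections 7.2.3 and 7.2.4 describe a market-ready device used to give a treatment. No section says that emission is on or off. If it is off, the client part of the point largely falls away.

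**The case against.** The best case for the plan has four parts.

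- *Section 8.3.1 is limited to users, and 6.3 discusses the eye hazard as a matter of client safety.* This is fair as far as it goes. It does not rescue 8.3.3, which has no such limit, and it sits badly with the expectation in 6.1.1 that users wear glasses.
- *The hazard is remote and mitigated.* The sponsor says the glasses are supplied to rule out any residual effect, and harm needs sustained direct viewing. This stands, and it is why the risk should be called low. A low, mitigated risk is still different from no risk.
- *The safety exceptions, the welfare commitment and adverse event handling (9.2) show that safety is managed.* They do. Managing a risk is not the same as disclosing it, and IRB review under 8.2.1 depends on the disclosure.
- *The appendices and consent pages were not available, and 8.3.1, 8.3.2 and 10 use subject to mean user.* This stands. Client coverage may exist in a form that was not seen. The visible steps still need either a client provision or a reference to one.

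A reader might go further and infer any of the following. The documents do not support them.

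- *Clients take part without consent.* This cannot be determined from the text available.
- *Every session exposes a client to a hazard.* The treatment is to the foot, the hazard is to the eye, and emission status is not stated.
- *The glasses are inadequate.* The protocol says they "block the laser light spectrum at OD 2+ @ 635nm, OD 0.75 @ 405nm VLT60", but gives no beam power or eye exposure against which to judge that rating.
- *Electric shock is an undisclosed study risk.* The warnings in 6.2 concern liquid, foreign material or immersion, and no study step introduces these.
- *Users are unqualified.* Section 6.1.1.1 requires applicable professional qualifications. They are untrained on this device only.

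Section 6.1.1 also expects users to be aware of client eligibility criteria. That describes the intended user and is not a study check of the acting clients.

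**Conclusion.** The point holds in two parts of different strength.

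The risk statements in 8.3.1 and 8.3.3 are wrong as written. This rests on the body text alone and on no assumption about emission. Ratings in Appendix A could show that the risk is small, but could not make both statements consistent with 6.3.

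The visible consent and eligibility steps cover users only, although clients are listed as subjects and receive the treatment. This is a gap in the body text that the sponsor may be able to close by reference. How much it matters depends on two unknowns: whether emission is on, and whether a client form exists in the appendices.

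The hazard is probably low. There is no effect on the Pass/Fail classification, the sample size or the qualitative analysis. The changes should still be made, because they are cheap and concern what participants and the IRB are told.

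One item stays a question only: 6.1.1 expects glasses on user and client, while 6.3 lists one client pair.

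**What to change.** 1. **Reword 8.3.1 and 8.3.3.** State a low optical risk to users and clients alongside the privacy risk, and name the mitigation: client glasses and observer intervention. If the consent form repeats the sentence in 8.3.1, make the same edit there.
2. **Extend 7.2.1, 7.2.2 and 8.2.1 to clients.** Add signed voluntary consent stating that refusal has no effect on employment, and an observer check against any labeled contraindications before treatment. Alternatively, state that emission is disabled during testing, or cite the client form if one exists.
3. **Ask the sponsor** whether users need eye protection during operation. No edit to 6.1.1 or 6.3 is proposed until that is answered.

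The cost is the rewording of two short sections, one short form and check per client, and an IRB notification. The observer already runs consent and qualification for users (6.4), so no staff or users are added. If emission is disabled or a client form exists, the client part takes one sentence.

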### **8.3.2. Potential Benefits of Participation**

There is no direct benefit to the subject (user) from participation in this Human Factors Validation Testing study. There may be benefit to potential future users of the device and to individuals with diagnosed toenail onychomycosis who may be potential future recipients of treatment with the Erchonia LunulaLaser™ OTC in the user settings.

### **8.3.3. Risk-Benefit Assessment**

The Risk-Benefit assessment reveals no negatives in conducting this Human Factors Validation Testing.

## **9. SAFETY MANAGEMENT**

### **9.1. USER DIFFICULTIES AND ERRORS**

All observed and reported user difficulties and errors will be recorded and evaluated as part of the study procedural protocol and consistent with the goal of this Human Factors Validation Testing.

### **9.2. ADVERSE EVENTS REPORTING**

While it is not anticipated that any adverse events will occur during this Human Factors Validation Testing, any and all potential adverse events observed or reported will be recorded on the applicable record forms and subsequently evaluated and handled in accordance with the study site, IRB and FDA reporting and handling policies and requirements.

## **10. PUBLICATION**

The outcome of this Human Factors Validation Testing will be written up for the purpose of inclusion in a 510(k) submission to the FDA seeking regulatory market clearance for OTC use of the Erchonia LunulaLaser™ OTC. In the event of inclusion of the outcome of this study in a potential future publication, there will be no identifiable information for any individual subject (user) and no individual case studies will be profiled.

## **11. ANALYSIS OF HUMAN FACTORS VALIDATION TESTING**

### **11.1. PRIMARY ANALYSIS**

A subject user in this study will be considered as either a study 'pass' or a study 'fail,' defined as follows:

- *Study Pass:* A subject user who satisfactorily completes both the device setup and treatment procedure will be determined a Study Pass.
- *Study Fail:* A subject user who does not satisfactorily complete either one or both of device setup and/or treatment procedure will be determined a Study Fail.

## **11.2. QUALITATIVE ANALYSIS**

The results of the Human Factors Validation Testing will be analyzed qualitatively to determine if the design of the device and all associated instructional materials and labeling require modification to reduce any identified use-related risks to acceptable levels.

### **11.2.1. Root Cause Analysis**

Observational and knowledge task data will be aggregated with the debriefing interview data and analyzed in detail to determine the root cause of any identified and/or reported use difficulties and/or errors, including close calls. The analysis will include evaluation of how the use errors or problems occurred within the context of device use, including the specific aspect of the user interface that caused problems for the user.

The root causes of all use errors and problems will be considered with respect to the associated risks to ascertain the potential for resulting harm and to consequently determine the need for and priority of implementing additional risk management measures.

### **11.2.2. Implementation of User Interface and Labeling Modifications**

In consideration of each risk identified through the root cause analysis as having the potential for resulting harm, user interface modifications and labeling and any other necessary risk management measures will be determined and implemented with the goal of reducing the risk to acceptable levels. This includes consideration of any suggestions for modifications to address used problem and/or errors made by the users during the post-test debriefing interview.

### **11.2.3. Retesting**

If indicated by the extent of user interface modifications and risk management strategies implemented, retesting may be performed to specifically address the aspects of the user interface that led to the use problems and errors and to evaluate the modified user interface elements to assess the risk management measures implemented in reducing risks to acceptable levels without introducing any new unacceptable risks.

